7.2 Informed Consent

All study procedures will be explained to every subject and their parent/guardian, and every parent/guardian will provide written consent to participate in this study prior to the performance of any study procedures.

7.3 Recruitment and Subject Screening

All patients at the Center for Pediatric Dentistry that meet the inclusion/exclusion criteria will be given the opportunity to participate in this research study. Each subject will be screened for compliance with the inclusion/exclusion criteria specified in section 6 prior to enrollment in this study.

7.4 Treatment Randomization

Restorations will be randomly allocated to a patient; all teeth in a single patient will be randomly allocated to receive one of the restoration treatments: 1) NuSmile Signature crowns (thirty patients in the intervention group 2) NuSmile ZR crowns (thirty patients in the intervention group and 3) and composite strip crowns (thirty patients in control group).

The randomization sequence will be created using STATA 12.0 (StataCorp, College Station, TX) statistical software using random block sizes, which are known only to the study statistician. The randomization list will be created and placed in the order determined above into opaque sealed envelopes prior to trial start. The envelopes will be kept in a secure place known only to the study coordinator, research assistants, and statistician.

Each patient will be assigned a random treatment when they arrive at the treatment appointment and after they have been determined eligible and have signed the consent form. The clinician will be told the treatment assignment immediately prior to the treatment appointment.

7.5 Operative Procedures

After the subject's parent/guardian has provided informed consent for participation in the study, patient's sedated procedure will be accomplished. This study will be executed within a comprehensive restorative treatment. A rubber dam will be placed and the crowns will be placed following manufacturers' guidelines, see below.

7.5.1 Crown Selection

The crown size is selected prior to prepping the tooth. The original size of the non-carious tooth is approximated and the crown size that appears most natural in the child's

mouth will be selected. For the NuSmile PVSSC Signature crowns, it is recommended to choose one to two sizes smaller than the size of a stainless steel crown (SSC) that would be deemed if used. Downsizing compensates for the additional thickness of the esthetic facing.

7.5.2 Preparation of the tooth

A) For NuSmile PVSCC Signature Crowns:

The tooth should be prepared to fit the crown so that the crown fits the tooth passively without using pressure. The incisal length of the tooth is reduced by approximately 2mm with the interproximal contacts opened. A feather-edge margin is created as far subgingivally as possible (approximately 1-2mm). The tooth is overall reduced by approximately 25-30%. For preparing the tooth subgingivally, and refining the preparation, tapered diamond burs may be used, proceeding from coarse to fine as the preparation is completed.

B) For NuSmile ZR Crowns:

The tooth should be prepared to fit the crown so that the crown fits the tooth passively without using pressure. The incisal length of the tooth is reduced by approximately 1.5-2mm with the interproximal contacts opened. With a coarse tapered bur, the tooth is overall reduced supragingivally by approximately 20-25%, or 0.5-1.25mm on all planes of the tooth. Reduction should follow the natural contours of the clinical crown and meet in a thin, tapered incisal edge. Carefully extend and refine the preparation margin to a feather-edge approximately 1-2mm subgingivally with a thin tapered diamond bur (green stripe 6852-012). Check that no subgingival ledges remain. Round all line angles and point angles of prepared teeth.

C) For Strip Composite Crowns:

The celluloid crown is selected based on the mesiodistal width of the tooth. The incisal length of the tooth is reduced by approximately 2mm with the interproximal contacts opened. A feather-edge margin is created supra or at gingival level. The tooth is overall reduced by approximately 15-20%. For preparing the tooth, and refining the preparation, tapered diamond or tungsten carbide burs may be used.

7.5.3 Crown Fitting, Adjustment and Cementation

A) For NuSmile PVSCC Signature Crowns:

In some cases, shortening the crown from the gingival margin may be necessary to achieve the desired results. The NuSmile Shortening Bur may be used at low range speed with a water spray to circumferentially reduce and feather the crown margins. After shortening, the composite polisher may be used to restore a polished surface to the esthetic facing.

A properly fitted crown will have a passive fit and be seated with finger pressure only. A "snap fit" is both undesirable and counter-productive as it may result in failure of the veneer. If the crown does not fit passively, the preparation must be refined to fit the crown. Crimping is not necessary, but if needed, excessive crimping or crimping near the facing must be avoided.

Clean the teeth of saliva, blood or debris and control gingival hemorrhage. NuSmile's Bio-active Resin Modified Glass Ionomer Cement will be used to cement the crowns according to the manufacturer's directions for use.

Once seated and after allowing enough time for the cement to set, a white stone or composite finishing bur may be used to equilibrate the veneer out of excessive occlusal contact in centric and excursion functions. The opposing teeth may be slightly adjusted, if needed.

It may be desirable to trim the veneer flush with the incisal edge if the patient demonstrates bruxism patterns or end-on occlusion. The distal point angle may be rounded to shape the crown for a right or left anterior.

B) For NuSmile *ZR* crowns:

Use NuSmile *Try-In* Crowns to test the fit and to avoid contamination with saliva or blood of NuSmile *ZR* Crown's prepared internal surface. If contamination with saliva or blood occurs, clean the internal surface of the NuSmile *ZR* Crown with Ivoclean or sandblast with aluminum oxide.

A properly fitted crown will have a passive fit and be seated with finger pressure only. A "snap fit" is both undesirable and counter-productive as it may result in fracture of the crown. If the crown does not fit passively, the preparation must be refined to fit the crown.

NuSmile *ZR* Crowns should only be adjusted with burs specifically designed for adjusting zirconia restorations taking care to use a light touch and a copious water spray. The NuSmile *ZR* Adjustment Burs can be used to circumferentially reduce and feather the crown margins when shortening a crown is necessary. The crown walls are very thin and should not be adjusted any more than 0.5mm in the incisal ½ of the proximal area as necessary. No other areas of the crowns should be adjusted. If adjustments are made, the *ZR* polishers should be used to restore a smooth surface to the crown.

Clean the teeth of saliva, blood or debris and control gingival hemorrhage. NuSmile's Bio-active Resin Modified Glass Ionomer Cement will be used to cement the crowns according to the manufacturer's directions for use.

C) For Strip Composite Crowns:

Trim the crown form and pierce one hole in the palatal incisal angle with a high-speed bur. Etch the enamel for approximately 20 seconds, wash and dry without desiccation of the dental structures. Apply a thin layer of bonding resin cure for 20 seconds ensuring that all surfaces are bonded equally. Fill celluloid crown with the appropriate shade of composite and seat with gentle, even, pressure, allowing excess to exit freely. Light-cure each tooth surface (labially, incisally and palatally) equally. Remove celluloid crown gently and adjust form and finish with either composite finishing burs or abrasive discs.

7.5.4 Failure to Fit

Teeth randomized for treatment will be included in the study even if they cannot accommodate the crown and therefore a composite crown is placed instead (intention-to-treat principle). The investigator will keep record of the teeth for further adjustment in the analysis. The reason for the fitting failure will also be recorded (See Appendix 2). If the tooth needs to be extracted (not matching inclusion/exclusion criteria), it will be excluded from the trial.

8. CLINICAL ASSESSMENTS

Clinical Assessments for both groups will be done at post crown placement (baseline); and months 3, 6, 12, and 18; and end of study visit occurring in range of 24 to 30 months from baseline. Please see Appendix 3 for scoring Criteria for the following:

- Fit
- Positioning
- Proximal Contact
- Marginal Adaptation
- Color: Match, staining/color change
- Gingival Status
- Retention of the crown
- Integrity of the veneer/composite
- Secondary Caries
- History of trauma
- Clinical pulp pathology
- Radiographical pulp pathology
- Parents' esthetic satisfaction

9. HUMAN SUBJECTS PROTECTION

Adverse Events (AE) will be documented as to onset, severity, duration, remedy, and relatedness to the test device and will be recorded on source documents and on case report forms. Any study staff member becoming aware of an AE must bring it to the attention of the Principal Investigator as soon as possible, and the Principal Investigator is responsible for reporting the Adverse Event, as needed, to the appropriate agencies and the study sponsor. AE reporting will follow the Western Institutional Review Board (WIRB) guidelines as below.

Adverse Events (AE) are any untoward or unfavorable medical occurrence in a human subject, including any abnormal sign (for example, abnormal physical exam or laboratory finding), symptom, or disease, temporally associated with the subject's participation in the research, whether or not considered related to the subject's participation in the research. Report to WIRB only AE that in the opinion of the investigator may **represent unanticipated problems involving risks to the other subjects in the research, as defined**:

- Event is **Unexpected** (in terms of nature, severity, or frequency) given (a) the research procedures that are described in the protocol-related documents, such as the IRB-approved research protocol and informed consent document, or the Investigator Brochure; and (b) the characteristics of the subject population being studied,
- **Related or possibly related** to participation in the research (possibly related means there is a reasonable possibility that the incident, experience, or outcome may have been caused by the procedures involved in the research); and
- Suggests that the research **places subjects or others at a greater risk of harm** (including physical, psychological, economic, or social harm) than was previously known or recognized.

If the adverse event is clearly not related to the study drug, device, procedures, or washout process, it would not represent a risk to other subjects in the research or a “problem” for the study and, therefore, does not have to be reported to WIRB.

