10. STUDY ASSESSMENTS

Clinical Assessments will be done at baseline post crown placement; at months 3, 6, 12 and 18; and end of study visit occurring in range of 24 to 30 months from baseline.

Assessments and documentation required at each assessment interval:

• Photographs of selected teeth	Baseline
• Photographs of tooth preparations	Baseline and when possible
• Photographs of cemented crowns	Baseline
• Photographs of occlusal and frontal views	Baseline and when possible
• Assessment of fit	All intervals
• Assessment of positioning	All intervals
• Assessment of proximal contact	All intervals
• Assessment of marginal adaptation	All intervals
• Assessment of color: match , staining/color change	All intervals
• Assessment of time placement	Baseline
• Assessment of gingival status	All intervals
• Assessment of retention	3, 6, 12, 18 and 24 mo
• Assessment of veneer/composite integrity	3, 6, 12, 18 and 24 mo
• Assessment of secondary caries	3, 6, 12, 18 and 24 mo
• Assessment of trauma	3, 6, 12, 18 and 24 mo
• Assessment of clinical pulp pathology	3, 6, 12, 18 and 24 mo
• Assessment of radiographic pulp pathology	24 mo
• Assessment of tooth	All intervals
• Assessment of parents' esthetic satisfaction	All intervals (baseline at 3-month follow up)

Non-recall assessment to be done at the time of tooth/crown lost to study due to trauma. If this was to occur, the patient would be discontinued from study and the justification recorded.

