11.0 DATA ANALYSIS

Descriptive statistics (means, standard deviations, counts, and percentages) will be calculated for all variables. To evaluate if the primary efficacy variables differ by the three treatment groups (NuSmile PVSCC Signature Crowns, NuSmile ZR, and Strip composite crowns), ANOVA or Chi-square tests of association will be performed.

All subjects evaluated at the 6-month interval or beyond and subjects who have lost crowns or teeth will be considered for efficacy. All enrolled subjects defined here as those who have had at least one crown placed will be evaluated for safety. Any missing, unused or false data will be omitted from data analysis.

The primary efficacy variables in this trial are fit, positioning, proximal contact, marginal adaptation, color match, gingival status, crown retention, veneer/composite integrity, secondary caries, occlusal integrity, history of trauma, clinical pulp pathology, parents' esthetic satisfaction. Scores for efficacy variables will be summarized and displayed using descriptive statistics (means, standard deviations, counts, and percentages).

Inferential statistics will be used to detect significant differences in the primary efficacy variables by the treatment status at baseline and at 6, 12, 18, and 24 month follow-up. Statistical differences will be calculated using logistic regression models accounting for within cluster variance using generalized estimating equations (GEE).

Safety variables include Adverse Events and Unanticipated Adverse Device Effects. All subjects that have had crowns placed will be evaluated for safety. Descriptions of occurrences, incidence, severity and required treatments for Adverse Events and Unanticipated Adverse Device Effects Will be summarized and tabulated where appropriate.

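### Adverse event incidence is to be reported, but no scheduled visit asks about adverse events and no rule links abnormal examination scores to adverse event records, so the figure may be incomplete and not comparable between arms

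*Combined protocol and SAP*

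**What the plan says.** Section 11.0 names AEs and Unanticipated Adverse Device Effects as the safety variables and undertakes to summarise "Descriptions of occurrences, incidence, severity and required treatments for Adverse Events and Unanticipated Adverse Device Effects". The safety population is every child with at least one crown placed.

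Section 9 defines an AE broadly, "including any abnormal sign (for example, abnormal physical exam or laboratory finding), symptom, or disease, temporally associated with the subject's participation in the research", with no requirement that it be thought related. It specifies what is written down once an event is known: "Adverse Events (AE) will be documented as to onset, severity, duration, remedy, and relatedness to the test device", on source documents and case report forms. On how an event comes to be known, it says only this: "Any study staff member becoming aware of an AE must bring it to the attention of the Principal Investigator as soon as possible".

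Section 10 sets out the "Assessments and documentation required at each assessment interval" in 19 lines, and Section 8 lists 13 assessments. Neither has an AE item. Section 10 does include items that can reveal harm, such as "Assessment of gingival status" at all intervals, and "Assessment of clinical pulp pathology" and "Assessment of secondary caries" at months 3, 6, 12, 18 and 24. Section 4 states that the trial is not blinded.

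**The concern.** An incidence is interpretable only if every child in the denominator had the same opportunity to have an event recorded. Here the denominator is fixed (all children with a crown), but for several kinds of event the numerator depends on a parent mentioning something or a staff member noticing it. Without a required entry, a child with no AE on file may have had no event or may never have been asked. Section 11.0 omits missing data, so the two cases would look the same in the tables.

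Three decisions lean on this. The trial compares two test crowns with composite crowns, and the safety summary will be read beside that comparison. Section 12.1 allows termination on discovery of an unforeseen risk. Section 12.2 lists an Unanticipated Adverse Device Effect as a reason for withdrawal. The last two depend on detection. Because staff know the restoration, the readiness to note or volunteer an event could also differ by arm.

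**Working it through.** The plan states no AE rate, capture rate or safety precision target, so there is no figure of its own to reproduce. The check is mainly a comparison of sections.

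**Step 1. Which events have a scheduled prompt?**

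| Event | Prompt in Sections 8 and 10 | Place in Section 11.0 |
|---|---|---|
| Gingival inflammation or bleeding | All intervals | Efficacy variable |
| Clinical pulp pathology, secondary caries, trauma, retention, veneer or composite integrity | Months 3, 6, 12, 18, 24 | Efficacy variables |
| Radiographic pulp pathology | Month 24 | In neither the efficacy nor the safety list |
| Pain or swelling that resolved between visits | None | AE, if someone reports it |
| Fragment swallowed or inhaled | None for the event; the missing material would show in the retention or integrity score | AE, if reported |
| Unscheduled dental or medical care | None | AE, if reported |
| Event during placement | Of the harm-type items above, only gingival status is scored at baseline | AE, if the operator reports it |

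The visits leave gaps of 3, 3, 6 and 6 months, then 6 to 12 months (month 18 to an end-of-study visit at 24 to 30 months). Apart from trauma, which Section 8 lists as a history item, the harm-type examinations score the state of the tooth and gum on the day.

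**Step 2. Do the scheduled scores reach the safety summary?** The Section 9 definition is wide enough to include an abnormal examination finding, but no section says that an abnormal score is to be entered as an AE. The populations differ too. Efficacy takes children assessed at month 6 or later and those who lost a crown or tooth; safety takes everyone with a crown. A child with an abnormal gingival score at month 3, crowns intact, who is then lost to follow-up is outside the efficacy population. That child enters the AE summary only if someone also files an AE. In the opposite direction, a finding filed as an AE and also scored would be counted in both summaries.

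**Step 3. Is relatedness usable in all arms?** Section 9 records relatedness to the test device. The control arm receives composite strip crowns, and the text does not say how relatedness is recorded there.

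**Step 4. Illustration of size.** Inputs from the plan: 30 children per arm, 90 in all (Section 5). The true risk and the capture probability c are assumptions.

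- Reported incidence = true risk × c. With c from 0.5 to 0.8, a true risk of 10% is reported as 5% to 8%, 20% as 10% to 16%, and 30% as 15% to 24%.
- With equal true risk but unequal capture, the apparent risk ratio is c1/c2. At 20% true risk, c of 0.9 and 0.6 gives 30 × 0.18 = 5.4 and 30 × 0.12 = 3.6 children, ratio 1.5. For c of 0.8 and 0.5 the counts are 4.8 and 3.0, ratio 1.6.
- With no events recorded and complete capture, the one-sided 95% upper limit is 1 − 0.05^(1/n): 9.5% for n = 30 and 3.3% for n = 90. Dividing by c gives the limit on the true risk: 11.9% and 4.1% at c = 0.8, 19.0% and 6.5% at c = 0.5.

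The limits at complete capture follow from the sample size alone. Everything else in this step depends on the assumed c.

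**The case against.** The strongest reply is that the main local harms are actively sought. Gingiva, pulp, caries, trauma and retention are examined on the same schedule in all arms with fixed scoring scales, and the AE definition covers abnormal examination findings. Telling the Principal Investigator is an escalation rule and is not stated to be the only means of collection. Placement is done under general anesthesia by study-trained clinicians, who would see a pulp exposure or soft-tissue injury and are bound by Section 9 to report it. A lost crown shows at the next retention score, and Section 10 adds an unscheduled assessment when a tooth or crown is lost through trauma. The case report forms are not among the documents and may contain an AE prompt.

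Much of this stands. A reader might infer that AEs are captured only by chance; the scheduled examinations show otherwise. A reader might infer that placement events depend on someone volunteering them; the operator observes them directly. A reader might also take it as established that the incidence will be too low and uneven by arm. Nothing in the documents shows this: they give no capture rate and no evidence of differential reporting, and Section 11.0 neither says that AEs are tabulated by arm nor plans an AE test.

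The reply does not close the gap for events outside the scored items, and it does not supply the missing link between scores and AE records. An AE prompt on an unseen form would help, but the protocol does not require one.

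**Conclusion.** The point holds in limited form. The plan promises an AE incidence without requiring that every child's family be asked, and without saying whether the scored abnormalities belong in it. The reported incidence may therefore be under-ascertained, and in a non-blinded trial it may not be comparable between arms. The gap mainly concerns resolved symptoms, swallowed or inhaled fragments, unscheduled care and placement events, plus abnormal scores in children who fall outside the efficacy population.

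The documents determine neither the size nor the direction of any error; the figures in the working show only what assumed capture rates would do. The efficacy comparison is not affected. The conclusion rests on reading Sections 8, 9, 10 and 11.0 as complete on AE collection. The change is worth making because it alters what is collected, and events not asked about at the time are hard to recover later.

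**What to change.** 1. Add a line to Section 10: *Adverse events since last contact: placement and all intervals*. Record it yes/no for every child, with the same standard question in all three arms, so that a negative answer is distinguishable from a question not asked.
2. State in Section 9 whether an abnormal scheduled score is also entered as an AE, and for which items and grades, to prevent both omission and double counting.
3. Record relatedness to the assigned restoration in every arm, including composite strip crowns, and not only to the test device.
4. State in Section 11.0 that AEs are tabulated by arm in the safety population.

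The cost is one short case report form page per visit. The downside is that more minor events will be recorded.

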10. STUDY ASSESSMENTS

Clinical Assessments will be done at baseline post crown placement; at months 3, 6, 12 and 18; and end of study visit occurring in range of 24 to 30 months from baseline.

Assessments and documentation required at each assessment interval:

• Photographs of selected teeth	Baseline
• Photographs of tooth preparations	Baseline and when possible
• Photographs of cemented crowns	Baseline
• Photographs of occlusal and frontal views	Baseline and when possible
• Assessment of fit	All intervals
• Assessment of positioning	All intervals
• Assessment of proximal contact	All intervals
• Assessment of marginal adaptation	All intervals
• Assessment of color: match , staining/color change	All intervals
• Assessment of time placement	Baseline
• Assessment of gingival status	All intervals
• Assessment of retention	3, 6, 12, 18 and 24 mo
• Assessment of veneer/composite integrity	3, 6, 12, 18 and 24 mo
• Assessment of secondary caries	3, 6, 12, 18 and 24 mo
• Assessment of trauma	3, 6, 12, 18 and 24 mo
• Assessment of clinical pulp pathology	3, 6, 12, 18 and 24 mo
• Assessment of radiographic pulp pathology	24 mo
• Assessment of tooth	All intervals
• Assessment of parents' esthetic satisfaction	All intervals (baseline at 3-month follow up)

Non-recall assessment to be done at the time of tooth/crown lost to study due to trauma. If this was to occur, the patient would be discontinued from study and the justification recorded.

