5. SAMPLE SIZE

As this is a pilot study, a sample size of 90 (30 in each arm) subjects will be chosen as a convenience sample. This is the number estimated to enroll in a 24 week period.

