6. STUDY POPULATION

Ninety (90) subjects contributing to approximately 120 to 200 crowns on primary teeth will be recruited from the patient pool of the Center for Pediatric Dentistry who receive care under general anesthesia and enrolled into the study. A maximum of four crowns will be placed in any subject. It is estimated that it will take approximately 24 weeks to place all crowns and complete the baseline examination.

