6.1 Inclusion Criteria

- Patients of record at the University of Washington's Center for Pediatric Dentistry
- Patients in general good health (ASA I)
- Patients aged 5 years old or younger
- Patients in need of at least one preformed crowns, on anterior primary teeth
- Patients undergoing general anesthesia for dental treatment
- Parent or guardian of patient able and willing to provide informed consent

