6.2 Exclusion Criteria

- Medically compromising condition
- Teeth with proximal space closures of sufficient magnitude to preclude placement of crown
- Teeth with complete absence of facial or lingual walls following tooth preparation
- Teeth that are expected to be exfoliated/extracted within one year will not participate in the study
- Anterior crowding
- Occlusion class III

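### No pre-placement score separates new pulp pathology or trauma from findings the tooth already had, and the sections disagree on whether a baseline score exists

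*Combined protocol and SAP*

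**What the plan says.** **Role of the outcomes.** Section 11.0 lists 13 primary efficacy variables, among them "history of trauma, clinical pulp pathology". Radiographic pulp pathology is not on that list.

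**Eligibility.** Section 6.1 admits "Patients in need of at least one preformed crowns, on anterior primary teeth" and sets no condition on pulp state or earlier injury. The nearest limit in Section 6.2 is "Teeth that are expected to be exfoliated/extracted within one year will not participate in the study". At surgery, Section 7.5.4 adds "If the tooth needs to be extracted (not matching inclusion/exclusion criteria), it will be excluded from the trial".

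**Timing.** The three sections differ:
- Section 10 schedules "Assessment of clinical pulp pathology" and the trauma score at 3, 6, 12, 18 and 24 months, and radiographic pulp pathology at 24 months only. Other rows of the same table are marked for baseline or for all intervals.
- Section 8 lists trauma history and both pulp items under visits that include baseline.
- Section 11.0 plans tests of the primary variables at baseline and at 6, 12, 18 and 24 months.

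Sections 8 and 10 both place baseline after crown placement.

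**Coding and analysis.** Appendices 11 to 13 grade each item Absent or Present. Section 11.0 specifies logistic regression with GEE by treatment. It gives no definition of a new event and names no entry-status covariate.

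**The concern.** The children need anterior crowns for multi-surface disease and are treated under general anesthesia, so some pulp involvement or past injury at entry is plausible in every arm. A tooth that already had the finding and still has it at follow-up is scored exactly like a tooth damaged after placement. Trauma is the clearest case: taken literally, a history of trauma that predates enrollment stays Present at every visit, whichever crown was placed.

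Two things are at stake. The event rate attributed to each restoration would be too high, and real differences between arms would be blurred. Section 7.5.2 plans different overall tooth reduction by arm (25–30%, 20–25% and 15–20%), so pulp outcome is a natural place to look for such a difference. Once a tooth is prepared and crowned, its entry state is hard to reconstruct.

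**Working it through.** **The plan's own figures.** Section 5: "a sample size of 90 (30 in each arm) subjects will be chosen as a convenience sample"; 3 × 30 = 90, which agrees. Section 6: "Ninety (90) subjects contributing to approximately 120 to 200 crowns on primary teeth"; 120/90 = 1.3 to 200/90 = 2.2 crowns per child, or 40 to 67 per arm. Section 7.4: "all teeth in a single patient will be randomly allocated to receive one of the restoration treatments", so the child is the randomized unit. The documents give no event rate, effect size, alpha or power, so there is no power figure to reproduce.

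**Is there an entry score?** Section 10 gives none before month 3. Section 8 and Section 11.0 imply one at baseline. Even if those two prevail, the score is taken after placement, and Section 11.0 does not use it to define or adjust the later outcome. On any reading, no pre-placement score is defined.

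**Effect of persisting findings.** Let q be the share of teeth with a pre-existing finding still scored Present at follow-up, taken as equal across arms, and p the rate of new findings among the rest.

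- Observed rate = q + (1 − q)p
- Observed difference = (1 − q)(p₂ − p₁)

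Assumed new-pathology rates are p₁ = 5% and p₂ = 10%:

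| q (assumed) | Arm 1 observed | Arm 2 observed | Difference (points) | Risk ratio |
|---|---|---|---|---|
| 0% | 5.0% | 10.0% | 5.0 | 2.00 |
| 2% | 6.9% | 11.8% | 4.9 | 1.71 |
| 5% | 9.75% | 14.5% | 4.75 | 1.49 |
| 10% | 14.5% | 19.0% | 4.5 | 1.31 |
| 20% | 24.0% | 28.0% | 4.0 | 1.17 |

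At q = 10% the lower rate is overstated 14.5/5 = 2.9 times, while the risk difference loses only half a point. The ratio is far more sensitive than the difference.

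**Power, for scale** (assumed two-sided alpha 0.05, one unit per child, 30 per arm, normal approximation). For 5% against 10%, power is about 11% at q = 0 and about 7% at q = 10%, so the trial could not detect that contrast in either case. For an assumed larger contrast, 5% against 30%, power falls from 73% at q = 0 to 61%, 51% and 37% at q of 5%, 10% and 20%.

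**The case against.** **A baseline score is not uniformly absent.** From the Section 10 table alone a reader might infer that these items are never scored at entry. The documents do not support that: Sections 8 and 11.0 point the other way. This stands, and the correct description is a conflict. It does not close the gap, because the implied score follows placement and has no role in the analysis.

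**Not every diseased tooth will score Present later.** A reader might infer that all entry disease becomes an outcome. Crowns are placed within comprehensive restorative treatment (Section 7.5), and teeth with short expected survival or needing extraction are removed. The documents do not say whether pulp disease is treated at that session or recorded; disease that resolves and later scores Absent adds nothing. This stands for pulp pathology, so the relevant q is persisting findings, not entry prevalence. It does not help for trauma read literally as a history.

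**Chance imbalance is not an extra bias.** With 30 children per arm, entry disease may differ between arms by chance, and a reader might call that a second bias. Children are randomized, so it is ordinary sampling error, which the test already allows for. It adds noise that an entry score could reduce, and no more is claimed.

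**Proportion.** This is a convenience-sample pilot, and the point touches two of 13 primary variables. That limits its weight but is no reason to skip an inexpensive repair.

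**Conclusion.** The concern holds in a limited form. Two primary efficacy variables have no pre-placement score, eligibility does not address them beyond expected loss or extraction, and neither the scales nor the model separates new from pre-existing findings. Sections 8, 10 and 11.0 also disagree on baseline scoring.

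The direction is established if persisting findings are equally common across arms: rates are overstated and the expected risk difference shrinks by (1 − q). The size is not established, because every value of q and p above is assumed. It could be negligible if q is near zero or if pulp disease is resolved at surgery. Without an entry score, the trial will be unable to say which. The change is worth making because it is inexpensive and cannot readily be made afterwards.

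**What to change.** 1. Reconcile Sections 8, 10 and 11.0 on whether trauma, clinical pulp pathology and radiographic pulp pathology are scored at baseline.
2. Score Appendix 11 and Appendix 12 for each study tooth before the randomization envelope is opened, for example at the Section 7.3 screening. Scoring before preparation is not enough: the trial is non-blinded (Section 4) and the clinician learns the arm just before the treatment appointment (Section 7.4). A score made knowing the arm could select teeth by arm.
3. Record from the operative note whether pulp treatment was given, as a descriptive item only. It arises after allocation, so it should neither define the analysis set nor enter the model.
4. In Section 11.0, define these outcomes as new pathology or new trauma in teeth scored Absent at entry, or keep all teeth and adjust the GEE for the pre-allocation entry score. For trauma the first option is safer: if history is read literally, every tooth Present at entry stays Present, and the adjusted logistic model may not converge.
5. For the 24-month radiographic score, use a pre-treatment radiograph only where one already exists. The documents do not say that one will.

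The cost is two tooth-level fields before allocation, one operative-note field and a sentence in Section 11.0, with no added visit or radiograph. The downside of restricting to teeth scored Absent is a smaller denominator for these outcomes.
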